4.8.9.2. Gynecological and Breast examination

Gynecological Examination is assessed at Screening, Month 3, Month 6 and Month 3 of Follow-Up period.

Breast examination (by palpation) will be performed at Screening, Month 6 and Month 3 FU visits.

Sponsor:	ObsEva		
Protocol:	18-OBE2109-002		
Document Version No.:	1.0	Document Date:	18-MAY-2021

A summary at each time point will be performed (number and percentage of subjects with normal, abnormal, abnormal significant) for Gynecological and Breast Examinations. Results will also be reported in listings.

4.8.10. **Columbia-Suicide Severity Rating Scale (C-SSRS)**

The C-SSRS questionnaire prospectively assess the occurrence of treatment-emergent suicidal ideation and behavior.

Subjects will complete:

- either the “Baseline” C-SSRS version, capturing lifetime history of suicidal ideation and behavior, for subjects under screening at the time of/after protocol amendment 3 implementation,
- or the “already enrolled subjects” C-SSRS version, for subjects already randomized at the time of protocol amendment 3 implementation, and who are providing answers to the C-SSRS for the first time during the study
- the “since last study visit” C-SSRS version, dedicated to subjects for whom the C-SSRS was completed at the previous study visit, for use at all remaining study visits.

The “Baseline” C-SSRS version is completed during Screening, or at Day 1 if not done during Screening.

The following C-SSRS data will be summarized by time point (baseline “Lifetime” or Prior to Study Entry, “Since Study Start” and each post-baseline time point):

The number of subjects experiencing the following, at any time post-baseline, will be summarized up to Month 6

- Any suicidal ideation or behavior
- Emergence of suicidal ideation.
- Worsening of suicidal ideation.
- Emergence of suicidal behavior.

Any suicidal ideation or behavior is defined as an answer “Yes” for at least one of five questions for suicidal ideation or for at least one of five questions for suicidal behavior.

Emergence of suicidal ideation/behavior is defined as having no suicidal ideation/behavior at baseline and having reported any type of suicidal ideation/behavior at any time post-baseline (including “Since Study Start” answers).

Worsening of suicidal ideation is defined to occur when the most severe suicidal ideation rating since study start at any time post-baseline is more severe than its rating at baseline. If data of suicidal ideation or behavior is missing at baseline then the subject will not be included in summaries of emergence or worsening of suicidal ideation or behavior. The “already enrolled subjects” C-SSRS version (“Prior to Entry Study”) will be used as baseline for subjects already randomized at the time of protocol amendment 3 implementation.

Sponsor:	ObsEva		
Protocol:	18-OBE2109-002		
Document Version No.:	1.0	Document Date:	18-MAY-2021

4.9. **Exploratory Analyses**

Bone turnover markers will be listed on the Safety Analysis Set.

Sponsor:	ObsEva		
Protocol:	18-OBE2109-002		
Document Version No.:	1.0	Document Date:	18-MAY-2021

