### 10.2.1 Screening Period – Screening visit

The subject will be informed of the study objectives and overall requirements, and written informed consent will be obtained before performing any study-specific procedures that are not standard of care.

The subject will be considered as included into the study after the ICF is signed and dated by the subject and the Investigator or legally acceptable designee.

For subjects who require washout for oral contraceptives, or other sex hormones, or GnRH antagonists/agonists (provided that the reason for discontinuing the previous GnRH-antagonist is not lack of efficacy), a period of up to 3 months will be allowed between signing the ICF and starting the collection of pain assessments in eDiary during the screening period. The screening period must cover two full menstrual cycles and will last about 3 months. During the screening period, the subject will be seen up to three times if not all screening assessments could be performed at the first screening visit (e.g. the endometrial biopsy must be performed after day 7 of the menstrual cycle).

During the screening period the following study screening assessments will be completed (see Schedule of Assessments in Appendix A):

- Demographic data, height and weight
- Medical and surgical history including concomitant diseases (and especially presence of rectovaginal endometriosis and adenomyosis), previous medication, obstetric/gynecological history and history of endometriosis including diagnosis and previous treatments for endometriosis.
- Assessment of DYS, dyspareunia and NMPP with the mB&B scale (see Appendix C). Answers will be captured in eCRF.
- Completion of the paper C-SSRS questionnaire “Baseline” version specific for subjects under screening (see Appendix R)
- ECG
- Physical examination
- Vital signs (blood pressure (BP) and heart rate)
- Urine pregnancy test
- TVUS of uterus and ovaries to measure endometrial thickness, to rule out any clinically significant gynecological conditions which might interfere with the study efficacy and safety objectives and to confirm that the subject has no ovarian endometrioma  $\geq 7$  cm in diameter
- Gynecological examination, including the mB&B scale (see Appendix C) clinical signs reporting (pelvic tenderness and pelvic induration)

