The efficacy variables planned in the protocol will not be analyzed due to the early study termination and the low number of subjects randomized.

2.5.2. **Pharmacokinetic Variables**

The pharmacokinetic variables planned in the protocol will not be analyzed due to the early study termination and the low number of subjects randomized.

2.5.3. **Safety Variables**

Safety endpoints include:

- Change from baseline to each scheduled assessment in BMD measured by DXA of lumbar spine (L1-L4), femoral neck, and total hip
- Incidence and severity of treatment emergent adverse events (TEAEs)
- Incidence and severity of hypoestrogenic TEAEs (hot flush)
- Time to the first post-treatment menses
- Changes in clinical laboratory assessments (hematology, biochemistry, coagulation parameters, hormones, lipids and urinalysis) from baseline to each scheduled assessment
- Any pathological changes from baseline in the endometrium as assessed by histology from endometrial biopsies
- Changes from baseline to each scheduled assessment in any other safety parameter including weight, vital signs, ECG, gynecological assessments and endometrial thickness

Safety analyses are described in Section 4.8.

Note that the endpoint “Time to the first post-treatment menses” was initially planned in the protocol, but will not be described in this SAP, because the study was stopped prematurely, and all subjects couldn’t be followed to evaluate this endpoint.

2.5.4. **Exploratory Variables**

The exploratory variables planned in the protocol will not be analyzed due to the early study termination and the low number of subjects randomized.

Sponsor:	ObsEva		
Protocol:	18-OBE2109-002		
Document Version No.:	1.0	Document Date:	18-MAY-2021

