4.8.5. Vital Signs and Physical Examinations

Vital signs include: Height (cm), Weight (kg), Body Mass Index, Systolic Blood Pressure (mmHg), Diastolic Blood Pressure (mmHg) and Heart Rate (beats/min).

Height is assessed at Screening; Weight is assessed at Screening, Month 6 and Month 6 of the follow-up period. Other Vital Signs are assessed at Screening, Day 1, every month during the treatment period and at Months 1 and 3 from the follow-up period.

Physical Examination is assessed at Screening, Months 3 and 6 of treatment and follow-up periods.

The actual value and change from Baseline to each on study evaluation will be summarized by treatment group and overall for vital signs.

By-subject listings of vital sign measurements will be presented in data listings.

Physical examination results at each time point will be summarized by treatment group and overall; shifts from Baseline in physical examination findings to each on study visit will also be presented. All physical examination findings will be presented in a data listing.

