- Table 14.4.9.2 ECG Findings up to Month 6 Follow-up – Safety Analysis Set
- Table 14.4.10.1 Gynecological Examination Findings by Visit from Day 1 to Month 6 Follow-up– Safety Analysis Set
- Table 14.4.11.2 Breast Examination Findings by Visit up to Month 6 Follow-up – Safety Analysis Set
- Table 14.4.12.1 Endometrial Biopsy Findings by up to Month 6 Follow-up– Safety Analysis Set
- Table 14.4.12.2 Endometrial Biopsy Diagnosis by Classification and Primary Diagnosis up to Month 6 Follow-up – Safety Analysis Set
- Table 14.4.13.1 Prior Medications – Safety Analysis Set
- Table 14.4.13.2 Prior Interventional Surgeries/Procedures for Endometriosis/ Endometriosis Symptoms – Safety Analysis Set
- Table 14.4.14.1 Concomitant Medications up to Month 6– Safety Analysis Set
- Table 14.4.14.2 Concomitant Medications from Month 6 to Month 6 FU – Follow-up Safety Analysis Set
- Table 14.4.15.1 Transvaginal Ultrasound: Uterus Length, Width, Depth, uterine Volume and Thickness up to Month 6 Follow-up – Safety Analysis Set
- Table 14.4.15.2 Transvaginal Ultrasound: Ovaries assessment up to Month 6 Follow-up – Safety Analysis Set

Sponsor:	ObsEva		
Protocol:	18-OBE2109-002		
Document Version No.:	1.0	Document Date:	18-MAY-2021

- Table 14.4.16.1 Suicide-related Treatment Emergent Events (C-SSRS) up to Month 6 – Safety Analysis Set
- Table 14.4.16.2 Suicide-related Events (C-SSRS) from Month 1 FU to Month 6 FU – Follow-up Safety Analysis Set

Post-text Listings

- Listing 16.1.7 Randomization scheme and codes (patient identification and treatment) - Randomized Set
- Listing 16.2.1.1 Subject Disposition and Study Termination Information – Part A - Randomized Set
- Listing 16.2.1.2 Subject Disposition and Study Termination Information – Part B - Randomized Set
- Listing 16.2.2.1 Inclusion Criteria – Screened Set
- Listing 16.2.2.2 Exclusion Criteria – Screened Set
- Listing 16.2.2.3 Protocol Deviations - Randomized Set
- Listing 16.2.3.1 Analysis Sets - Randomized Set
- Listing 16.2.3.2 Subjects with actual treatment not corresponding to any of the planned treatment groups - Safety Analysis Set
- Listing 16.2.4.1 Demographic and Baseline Information – Randomized Set
- Listing 16.2.4.2 Menstrual Cycle – Randomized Set
- Listing 16.2.4.3 Biberoglu & Behrman at Screening – Randomized Set
- Listing 16.2.4.4 Pelvic Pain Scores and Analgesic Use at Baseline – Randomized Set
- Listing 16.2.4.5 Endometriosis History – Randomized Set

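### SAP 2.5.3 keeps change from baseline in gynecological assessments as a safety endpoint, but no table shows within-woman change in the gynecological examination

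*SAP*

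**What the plan says.** SAP 2.5.3, repeating Protocol 7.2, lists among the retained safety endpoints: "Changes from baseline to each scheduled assessment in any other safety parameter including weight, vital signs, ECG, gynecological assessments and endometrial thickness".

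The analysis for the gynecological and breast examinations is in SAP 4.8.9.2. It first gives the schedule: "Gynecological Examination is assessed at Screening, Month 3, Month 6 and Month 3 of Follow-Up period". It then gives the analysis: "A summary at each time point will be performed (number and percentage of subjects with normal, abnormal, abnormal significant) for Gynecological and Breast Examinations". Listings are added. No shift or change from baseline is mentioned.

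The matching output in SAP Appendix B is "Table 14.4.10.1 Gynecological Examination Findings by Visit from Day 1 to Month 6 Follow-up". The parallel breast table is "Breast Examination Findings by Visit up to Month 6 Follow-up", with no Day 1 start.

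For the physical examination, SAP 4.8.5 goes further: "shifts from Baseline in physical examination findings to each on study visit will also be presented". That output is Table 14.4.8.2.

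SAP section 5, which records departures from the protocol, names one dropped safety endpoint: time to first post-treatment menses.

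**The concern.** The endpoint concerns change within a woman. The planned table is a separate snapshot at each visit. Where some women already have an abnormal pelvic finding at Screening, the percentage abnormal at Month 3 or Month 6 mixes findings that persisted with findings that are new, and it hides those that resolved. The women examined at later visits are also a smaller and possibly different group from those at Screening, so a change in the percentage may partly reflect who remained.

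At stake is whether a reader of the study report can see, by arm, how many women developed a new or worsened finding on treatment without working through a listing by hand. The table title adds a smaller problem: read literally, it leaves out the only pre-dose examination.

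**Working it through.** The documents give no figure to reproduce. The check sets the passages side by side and then asks what two by-visit percentages can identify.

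**Step 1. Items in the SAP 2.5.3 endpoint against their planned outputs**

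| Item | Change or shift from baseline? | Where |
|---|---|---|
| Weight, vital signs | Yes, change | SAP 4.8.5, Table 14.4.7.1 |
| ECG | Yes, change in values | SAP 4.8.6, Table 14.4.9.1 |
| Endometrial thickness | Yes, change | SAP 4.8.8, Table 14.4.15.1 |
| Uterine dimensions and volume on ultrasound | Yes, change | SAP 4.8.8, Table 14.4.15.1 |
| Gynecological examination | No, by-visit counts only | SAP 4.8.9.2, Table 14.4.10.1 |

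The general clause in SAP 4.2.1 allows change from baseline where applicable, but no listed gynecological or breast output uses it.

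**Step 2. Baseline.** SAP 4.2.11 makes the last pre-dose value the baseline where no specific rule exists. SAP 4.8.9.2 and Protocol Appendix A place the pre-dose gynecological examination at Screening, with none on Day 1. A baseline value is therefore collected. SAP 4.5.2 tabulates it by arm, separately from the later visits.

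**Step 3. What two percentages identify.** Take *n* women examined at both visits, *a* abnormal at Screening and *b* abnormal later. The number newly abnormal lies between max(0, *b* − *a*) and min(*b*, *n* − *a*). All inputs below are assumed.

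- *n* = 20, *a* = 4, *b* = 4: from max(0, 0) = 0 to min(4, 16) = 4. Both visits read 20%.
- *n* = 20, *a* = 4, *b* = 6: from max(0, 2) = 2 to min(6, 16) = 6.
- 40% at both visits: from 0% to min(40%, 60%) = 40%.
- 50% then 40%: from 0% to min(40%, 50%) = 40%.
- 30% at both visits: from 0% to min(30%, 70%) = 30%.

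A net rise sets a lower bound, but the number of new findings is not identified. These bounds need both percentages to come from the same women.

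**Step 4. Are they the same women?** Not necessarily. SAP 4.2.10 uses an early-discontinuation examination only within 14 days of a visit at which it was planned. For the treatment-period examinations this means Days 71 to 99 (85 ± 14) or Days 155 to 183 (169 ± 14). Women withdrawing outside those windows drop out of the by-visit rows. Protocol 13.5 planned baseline means matched to the women attending each visit; SAP 4.2.1 keeps that only for bone mineral density.

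**The case against.** The case on the other side is substantial, and several stronger readings fail against it.

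- **A reader might infer that 4.8.9.2 ignores baseline and starts at Day 1.** It does not. It names Screening and summarizes each time point. The Day 1 start is only in the title of Table 14.4.10.1 and looks like a wording slip.
- **A reader might infer that new abnormalities cannot be seen.** They can. Listing 16.2.9.4 gives each woman's results. Protocol 12.1.2 and 12.1.3 send clinically significant new findings and worsened baseline conditions to adverse events. This stands, with a limit: Protocol 12.1.4 keeps worsening endometriosis out of adverse events unless it is clinically significant and out of keeping with the expected course. It relies on efficacy assessment to capture the rest, and SAP 4.6 now only lists efficacy data.
- **A reader might infer that the endpoint is not produced at all.** Part of it is. Gynecological assessments can include the ultrasound, for which SAP 4.8.8 plans changes from baseline in uterine measures and endometrial thickness. Only the examination result lacks a paired display.
- **A reader might infer that a promised shift table was dropped.** Protocol 13.5.5 calls for change from baseline only where applicable and specifies shifts only for laboratory parameters. What stands is narrower: a retained endpoint has no matching output for the examination, and section 5 does not say so.
- **A reader might assume that the pelvic examination is usually abnormal at baseline and the physical examination usually normal.** The documents give no rates. Protocol 10.2.1 does attach to the screening gynecological examination "clinical signs reporting (pelvic tenderness and pelvic induration"), but these signs are scored on the modified Biberoglu and Behrman scale. Nothing says that scoring them makes the examination result abnormal.

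Finally, in a small, descriptive safety report, reading one listing is feasible. That limits the severity but does not replace a summary by arm.

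**Conclusion.** The point holds in a limited form. For the gynecological examination, the planned tables do not give change within subject, so new or worsened findings are not tabulated by arm. They must be recovered from Listing 16.2.9.4 or, where judged clinically significant, from adverse events. Section 5 is silent on this, and the title of Table 14.4.10.1 does not match the examination schedule.

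The effect is modest. SAP 1.2 confines the report to safety after early termination with far fewer women than planned, the safety analysis is descriptive, and no primary conclusion depends on this table. The conclusion that by-visit percentages do not identify new findings needs no assumed rate. The counts and the 30% to 50% figures used above are illustrative only and apply when both percentages come from the same women.

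**What to change.** - In SAP 4.8.9.2, add a shift table for the gynecological examination (normal, abnormal, abnormal significant) from Screening, as the last pre-dose value, to Month 3, Month 6 and Month 3 follow-up. Present it by arm, in women with both examinations, as SAP 4.8.5 does for the physical examination. List it in Appendix B.
- Retitle Table 14.4.10.1 so that it includes Screening.
- If the shift table is not added, declare the omission in SAP section 5.
- A breast shift table is optional, because the endpoint does not name breast examination. It would run from Screening to Month 6 and Month 3 follow-up only, as no breast examination is scheduled at Month 3.

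The cost is one table, or two with breast, from data already collected, using the physical-examination shift table as the template. Withdrawal examinations outside the 14-day windows would still appear only in the listing.

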#### Withdrawal during treatment period:

Subjects who discontinue between Day 1 and Month 3 should undergo the procedures required at Month 6 (except the DXA scan and the endometrial biopsy if a biopsy was obtained at screening) and will not enter the 6-month follow-up period.

Subjects discontinuing the study treatment between Month 3 and Month 6 should undergo the procedures required at Month 6. These subjects will enter a 6-month follow-up period and will continue daily eDiary recording for 6 months and up to Month 6 FU visit in order to continue to collect efficacy data.

PK sampling is not required if the subject had no IMP administration the day prior to the withdrawal visit.

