For other safety results, data from early discontinuation should be compared to theoretical visits dates. Only assessments within the window of theoretical date +/-14 days will be used for analyses, if it is planned to have a such assessment at this visit and no other assessment is in the window. If a subject discontinued in the main treatment period, date will be compared to the theoretical visit dates in main treatment period as described in Table 3. If a subject discontinued in the follow-up period, date will be compared to the theoretical visit dates in Follow-up period from

Sponsor:	ObsEva		
Protocol:	18-OBE2109-002		
Document Version No.:	1.0	Document Date:	18-MAY-2021

Table 4.

For unscheduled safety assessments, if the assessment occurs in a window of +/- 14 days of a planned eCRF visit for which it was planned per protocol to have such assessment, and no assessment was done for that visit, the assessment will be assigned to that visit. If the assessment is equally distant from two eCRF visits with no corresponding safety assessment, the assessment will be assigned to the next visit.

For biopsy, DXA assessment or laboratory assessment, if an assessment has been assigned in external data to a follow-up visit of the main study for subjects entered extension study, the visit of assessment should be reassigned with the same rules described above for unscheduled safety assessment.

Table 3 Theoretical Visit Dates in Main Treatment Period

Visit	Theoretical Date
Month 1	Day 29
Month 2	Day 57
Month 3	Day 85
Month 4	Day 113
Month 5	Day 141
Month 6	Day 169

Sponsor:	ObsEva		
Protocol:	18-OBE2109-002		
Document Version No.:	1.0	Document Date:	18-MAY-2021

Table 4 Theoretical Visit Dates in Follow-up

Visit	Theoretical Date
Month 1 FU	Month 6 date or treatment discontinuation date + 28
Month 2 FU	Month 6 date or treatment discontinuation date + 56
Month 3 FU	Month 6 date or treatment discontinuation date + 84
Month 4 FU	Month 6 date or treatment discontinuation date + 112
Month 5 FU	Month 6 date or treatment discontinuation date + 140
Month 6 FU	Month 6 date or treatment discontinuation date + 168

4.2.11. **Baseline Definition**

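### SAP 4.2.10, read literally, keeps some early-discontinuation C-SSRS interviews out of rows that SAP 4.8.10 defines as covering any time after baseline

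*SAP*

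**What the plan says.** SAP 4.8.10 introduces the suicidality rows with "The number of subjects experiencing the following, at any time post-baseline, will be summarized up to Month 6". The rows are any ideation or behavior, emergence of ideation, worsening of ideation, and emergence of behavior. Emergence means none at baseline and "having reported any type of suicidal ideation/behavior at any time post-baseline". Worsening likewise takes the most severe post-baseline rating.

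SAP 4.2.10, under other safety data, sets a different rule for women who stop early: "For other safety results, data from early discontinuation should be compared to theoretical visits dates". It continues: "Only assessments within the window of theoretical date +/-14 days will be used for analyses", and adds a condition: "if it is planned to have a such assessment at this visit and no other assessment is in the window". SAP Table 3 puts the theoretical visits at Days 29, 57, 85, 113, 141 and 169.

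The protocol makes sure that such interviews exist. Section 10.7.2 states: "Subjects who discontinue between Day 1 and Month 3 should undergo the procedures required at Month 6". The only exceptions are the DXA scan and, in some cases, the biopsy. Women who stop between Month 3 and Month 6 also have the Month 6 procedures. Section 10.2.2.5 includes the C-SSRS among these procedures, and Appendix A schedules it at every monthly visit.

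**The concern.** A rule that keeps one value per visit suits by-visit summaries. It does not suit a count of women who ever reported something, where every record should be eligible. Because the C-SSRS is monthly, a woman who leaves soon after an attended visit already has an interview in the only window that covers her withdrawal interview. A woman who leaves in the first two weeks is covered by no window.

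Later interviews would not recover the answer. After the first completion, the protocol (10.4.10) uses the form that asks about the period since the last study visit. Women who stop before Month 3 do not enter follow-up, so for them the withdrawal interview is the last one planned. Since early termination, SAP 1.2 has made safety reporting the purpose of the analysis. With few subjects, one omitted positive answer can turn a one into a zero.

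**Working it through.** The documents give no share of interviews lost, so there is no planned figure to reproduce. The check is a day count.

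**Inputs**
- Theoretical visit days: D(k) = 28k + 1 for k = 1 to 6, giving 29, 57, 85, 113, 141 and 169. This matches SAP Table 3 and protocol 10.2.
- Window: D(k) - 14 to D(k) + 14 (SAP 4.2.10).
- C-SSRS at every monthly visit (protocol Appendix A) and at withdrawal (protocol 10.7.2 with 10.2.2.5).
- Withdrawal day: not given. Base assumption: uniform over Days 2-168, with every scheduled C-SSRS done on its theoretical day.

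**Step 1: windows.** They are 15-43, 43-71, 71-99, 99-127, 127-155 and 155-183.

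**Step 2: which interviews are unused.** An interview on day t is used if some D(k) satisfies |t - D(k)| <= 14 and no earlier C-SSRS lies in that window.
- Days 2-14: no window, so unused.
- 1-13 days after a completed visit: only the window of that visit applies, and it is filled, so unused.
- 14 days after a completed visit: the next window has opened and is free, so used.
- On a visit day, or 1-14 days before it: used.

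**Step 3: count.** Unused days are 2-14, 30-42, 58-70, 86-98, 114-126 and 142-154. That is 13 + 5 × 13 = 78. Days 2-168 number 167, and 78/167 = 46.7%.

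**Step 4: vary the assumptions**

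| Assumption | Share unused |
|---|---|
| Base case | 78/167 = 46.7% |
| Visits shifted at random by up to 3 days (simulated) | 47.1% |
| Withdrawal on Days 15-168 only | 65/154 = 42.2% |
| Front-loaded: daily weight 0.5^(t/h), h = 30, 60, 120 days | 54.5%, 50.6%, 48.6% |
| Fraction s of withdrawals at a scheduled visit: 46.7% × (1 - s), s = 0.25, 0.5, 0.75, 1 | 35.0%, 23.4%, 11.7%, 0% |
| Only 75% or 50% of scheduled C-SSRS done (simulated with the shift above) | 37.4%, 27.5% |

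The last row can be checked by hand without the shift: (13 + 0.75 × 65)/167 = 37.0% and (13 + 0.5 × 65)/167 = 27.2%. In principle, timing alone could put the share anywhere from 0% (all withdrawals at visits or in the 14 days before) to 100% (all within 1-13 days after a completed visit).

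**The case against.** The strongest reply is that the specific text governs. SAP 4.8.10 states its own scope, and 4.2.10 is a section about allocating results to visits, so a sensible programmer would apply the windows only to by-visit displays. That reading is arguable and may be what was intended, but the SAP does not state it. Section 4.2.10 speaks of use in analyses without limiting itself to by-visit summaries, whereas a note in 4.2.12 does limit itself in that way. Section 4.8.4 expressly brings unscheduled values into the laboratory shifts, and 4.8.10 has no such wording. It also places by-time-point summaries and ever-counts together, so one windowed dataset could feed both.

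Some mitigation stands. The interview remains in Listing 16.2.9.13. An event also reported as an adverse event is tabulated by onset date through 30 days after discontinuation (SAP 4.8.2), independently of these windows. The C-SSRS arrived with protocol amendment 3 (SAP 4.8.10), so women randomized before then have earlier visits with no C-SSRS to fill a window, which lowers the share unused.

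**Conclusion.** The two SAP sections conflict, and the literal rule leaves out withdrawal interviews on Days 2-14 or 1-13 days after a completed monthly C-SSRS. For the any, emergence and worsening rows the effect runs one way: removing a record cannot add a positive answer. A count changes only if the removed interview held the woman's sole positive or worst answer. The size is conditional: 47% of withdrawal days under the base assumptions, with the alternatives in the table above.

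A reader might infer more than the documents support:
- **That about half of all withdrawal interviews are lost.** This needs withdrawals spread between visits and complete scheduled C-SSRS. Neither is documented.
- **That unscheduled interviews are excluded too.** The unscheduled paragraph of 4.2.10 only says when a result is assigned to a visit. It does not bar unassigned results from analysis.
- **That women still on treatment at early termination ended at such a visit.** The documents do not describe how they left.
- **That the table is shown to be biased.** The wording permits under-counting. It does not show that any positive answer was lost.

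**What to change.** Add one sentence to SAP 4.8.10. The any-time, emergence and worsening rows use every C-SSRS after the first dose up to Month 6 or, for early stoppers, up to and including the early-discontinuation visit, whether scheduled, unscheduled or early-discontinuation, regardless of the 4.2.10 windows. Those windows then apply only to by-visit rows.

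The end point needs to be explicit. Without it, follow-up interviews would enter the treatment-period table. The withdrawal visit must be named because SAP 4.2.12 ends the main treatment period at the discontinuation date, and the interview may come later. Apply the same rule within the follow-up period for Table 14.4.16.2.

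The cost is one sentence and a small programming change, with no new data. If this was already the intention, the sentence simply records it.
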